4.1 Inclusion Criteria

Subject must fulfill all of the following criteria at Screening and on Day 1 to be eligible for inclusion in the study:

Inclusion Criteria:

1. Male or female adult subjects 18 years of age and older.
2. Confirmed diagnosis of Type I or Type II diabetes mellitus (DM). Any of the following are sufficient:
 - Current regular use of insulin for the treatment of diabetes
 - Current regular use of oral anti-hyperglycemia agents for the treatment of diabetes
 - Documented diabetes by American Diabetes Association and/or World Health Organization (WHO) criteria
3. BCVA, using Standard Early Treatment Diabetic Retinopathy Study (ETDRS) chart, of ≥ 19 letters ($\sim 20/400$) and ≤ 73 letters ($\sim 20/40$) in the study eye and ≥ 34 letters ($\sim 20/200$ or better) in the fellow eye at Screening and Day 1.
4. Presence of ciDME in the study eye defined as Heidelberg Spectralis Optical Coherence Tomography (SD-OCT) CST ≥ 305 μm in women and ≥ 320 μm in men in the study eye (as assessed at Screening by the Investigator and Central Image Reading Center (CIRC) and on Day 1 by the Investigator).
5. Subjects' first anti-VEGF injection in the study eye occurred ≤ 36 months prior to Day 1.
6. Subjects have received at least 3 anti-VEGF injections in the study eye within a 6-month period within the 36 months prior to Day 1.
7. The last anti-VEGF injection in the study eye is ≥ 8 weeks prior to Day 1.
8. Subjects, who in the view of the Investigator, are able to defer treatment in the study eye for at least 6 months following Day 1. Note, rescue treatment is available (see Section 5.8).
9. Values for blood and urine safety labs at the Screening visit showing no clinically significant deviation as determined by the Investigator.

10. Women who are post menopausal for at least 1 year, surgically sterile for at least 3 months prior to Day 1, or who are agreeable to using highly effective contraception (adequate contraceptive measures include stable use of oral contraceptives or other prescription pharmaceutical contraceptives for two or more menstrual cycles prior to screening; IUD; bilateral tubal ligation; vasectomy; condom plus contraceptive sponge, foam, or jelly or diaphragm plus contraceptive sponge, foam, or jelly), or abstinence.
11. Sexually active men who are not vasectomized and have sexual partners of childbearing potential should be agreeable to using highly effective contraception.

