7.2.1 Screening Phase (Weeks -4 to Day -1 [Visit 1])

Subjects will undergo screening during a visit that can occur up to 4 weeks prior to the Day 1 Visit. Following full discussion of the study and the signing of ICF, a screening subject ID number will be assigned. All subjects will be assessed for eligibility against the inclusion and exclusion criteria.

The following screening and baseline assessments will be performed:

- Obtain subject's full medical history, including ophthalmic ocular history with DME disease history, concomitant illnesses/diseases and medications, therapies and supplements taken within the past 3 months, previous participation in interventional clinical studies in the past three months;
- Record demographic information including race, ethnicity and date of birth;
- Conduct the following ophthalmic measurements and examinations in both study eye and fellow eye in accordance with procedures as described in Section 6.3.7;
 - BCVA;
 - Slit lamp biomicroscopy;
 - IOP (prior to dilation);
 - Dilated indirect ophthalmoscopy;
 - Fundus photography;
 - SD-OCT;
- Collect blood and urine samples per Section 6.3;
- Perform measurements of height (meters [m], without shoes) and weight (kilogram [kg], without shoes or overcoat). Calculation of body mass index (BMI) will be automated in the database;
- Vital signs (Blood pressure [BP], PR, respiratory rate, and body temperature [°C])
 - BP and PR will be recorded after subject has been supine for 5 minutes;
- Urine pregnancy test (women of childbearing potential);

- Perform eligibility check, evaluating all results of the screening assessment results against the inclusion and exclusion criteria;
- All AEs reported after signing of the ICF will be recorded;
- Review the study procedures and study visit schedule with the subject.

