8.5.1 Primary Efficacy Analysis

The primary efficacy endpoint is change from baseline in BCVA letter count in the study eye at Week 16. Change from baseline in BCVA letter count will be calculated as Week 16 BCVA letter count minus Day 1 BCVA letter count such that a negative difference indicates a worsening in vision. In addition, treatment comparisons between each dose of the KVD001 Injection and the sham will be calculated as KVD001 Injection minus sham, such that a positive result indicates more letters gained in the KVD001 Injection treatment group.

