8.5.1.2 Statistical Methods

The study eye ETDRS letter scores including changes from baseline will be summarized using continuous descriptive statistics. An analysis of covariance (ANCOVA) model will be used to compare the change from baseline in BCVA letter count at Week 16 between each dose of the KVD001 Injection and the sham. The ANCOVA model will include treatment as a main effect and baseline BCVA letter count as a covariate. Least-squares means (LSMeans) for each treatment group, the LSMean difference between each dose of the KVD001 Injection group and the sham group, the corresponding CIs and the p-values will be presented.

As a sensitivity analysis, treatment group differences for changes from baseline in BCVA letter count will be evaluated using a mixed model repeated measures (MMRM) ANCOVA fitted with treatment group, visit and the treatment by visit interaction as categorical variable terms with baseline BCVA letter score and baseline CST as covariates with contrasts included for each visit. LSMeans and 95% confidence intervals for each treatment group, the LSMeans difference between each dose of the KVD001 Injection and sham, the corresponding confidence intervals, and the p-values will be presented for each visit.

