8.8 Determination of Sample Size

The proposed sample size (41 per treatment group) will provide approximately 80% power to detect a difference in change from baseline of 5 letters between either of the KVD001 treatment groups and sham based on a two-sided, two-sample t-test with significance level 0.05 and assuming a pooled SD of 7.5 letters.

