8.3 Definition of Baseline

The baseline assessment will be the latest, valid pre-dose assessment available. Laboratory data may not be used from hemolyzed samples, mishandled samples, quantity not sufficient, or other conditions that would render the values invalid.

[figure not shown]

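### Screening BCVA is collected but is not a covariate in the Protocol's primary ANCOVA or the visible MMRM; prespecifying it is a cheap, optional precision gain of uncertain size

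*Protocol*

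**What the plan says.** Protocol 8.5.1.2 specifies the primary ANCOVA: "The ANCOVA model will include treatment as a main effect and baseline BCVA letter count as a covariate". SAP 8.3 defines the covariate: "The baseline assessment will be the latest, valid pre-dose assessment available". Protocol 8.2 has the same rule. Protocol 8.5.1 defines the endpoint as "Week 16 BCVA letter count minus Day 1 BCVA letter count".

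A second pre-treatment reading is scheduled. Protocol 7.2.1 instructs sites at Screening: "Conduct the following ophthalmic measurements and examinations in both study eye and fellow eye in accordance with procedures as described in Section 6.3.7". BCVA heads the list that follows, and Table 2 marks it for the study eye at both Screening and Day 1. Inclusion criterion 3 applies its letter limits at both visits; its closing words are "in the fellow eye at Screening and Day 1". On the gap between the readings, Protocol 7.2.1 says: "Subjects will undergo screening during a visit that can occur up to 4 weeks prior to the Day 1 Visit".

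The MMRM sensitivity analysis (Protocol 8.5.1.2, SAP 13.2) adjusts for baseline BCVA and baseline CST only. SAP section 1 says that its methods supersede the Protocol's. The visible text of SAP 13.1 names an ANCOVA but no covariates, and the model code and its definitions are redacted. SAP section 16, which lists changes from the Protocol's analyses, mentions no covariate change.

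**The concern.** A single ETDRS letter score contains test-retest error. When two readings are taken before randomization, the second can help separate an eye's underlying level from that error, and so predict Week 16 better than Day 1 alone. A model that omits it may leave removable noise in the residual.

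The stake is precision. The primary comparisons rest on 41 eyes per arm and a 5-letter difference. A second baseline covariate would leave the endpoint and the treatment contrast as they are and needs no new data. It could also serve the MMRM and the BCVA analyses at other visits.

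**Working it through.** **The plan's own figure.** Protocol 8.8 states: "The proposed sample size (41 per treatment group) will provide approximately 80% power to detect a difference in change from baseline of 5 letters", "based on a two-sided, two-sample t-test with significance level 0.05 and assuming a pooled SD of 7.5 letters". With n = 41 per arm, difference 5, SD 7.5 and two-sided alpha 0.05, the noncentral t with 80 df gives 84.7% power (normal approximation 85.5%). On these inputs 37 per arm gives 80.8%, so the stated 80% is conservative. The sample size does not rely on covariate adjustment.

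**Current precision.** Take 7.5 letters as the residual SD of the one-covariate model, with 123 − 4 = 119 df. Half-width = t(0.975, 119) × 7.5 × √(2/41) = 1.980 × 7.5 × 0.2209 = 3.28 letters. Power at 5 letters is 84.9%.

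**What decides the gain.** The ratio of residual variances, two covariates to one, is 1 − p², where p is the partial correlation of Screening with Week 16 BCVA given Day 1. The documents give neither p nor the correlations behind it, so assumptions are needed.

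**Measurement-error model.** Assumptions:
- between-eye SD b of 9 to 15 letters
- test-retest SD e of 3 to 5 letters, independent at each visit
- true Screening-to-Day 1 change with SD d of 0 to 3 letters
- SD of the Day 1-to-Week 16 change 7.5 (the plan's figure), so the true-change variance is 56.25 − 2e²

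Largest gain (b = 15, e = 5, d = 0):
- Week 16 variance = 225 + 6.25 + 25 = 256.25
- given Day 1: 256.25 − 225²/250 = 53.75
- given both readings: 256.25 − 225²/237.5 = 43.09
- reduction = 1 − 43.09/53.75 = 19.8%

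Smallest gain (b = 9, e = 3, d = 3):
- Week 16 variance = 81 + 9 + 38.25 + 9 = 137.25
- given Day 1: 137.25 − 90²/99 = 55.43
- covariance of Screening with Week 16 given Day 1: 81 − 81 × 90/99 = 7.36
- variance of Screening given Day 1: 90 − 81²/99 = 23.73
- reduction = (7.36²/23.73)/55.43 = 4.1%

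With e = 2 the reduction is 1.4% to 3.5%. With e = 3 and d = 5 it is about 2% to 3%.

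**Effect on the primary comparison** (118 df, reduction applied to SD 7.5):

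| Variance reduction | Residual SD | 95% CI half-width | Power at 5 letters |
|---|---|---|---|
| 0% | 7.50 | 3.28 | 84.9% |
| 4% | 7.35 | 3.21 | 86.3% |
| 10% | 7.12 | 3.11 | 88.4% |
| 20% | 6.71 | 2.93 | 91.7% |

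With 80 df each power is 0.2 to 0.3 points lower (84.7%, 86.1%, 88.2%, 91.5%). In sample-size terms, 41/0.96 − 41 ≈ 2 and 41/0.80 − 41 ≈ 10 subjects per arm.

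**Check on another structure.** Here the correlations are set directly, in the order Screening–Day 1 / Day 1–Week 16 / Screening–Week 16.
- All equal to ρ: the ratio is (1 + 2ρ)/(1 + ρ)². Reductions run from 11% (ρ = 0.5) to 22% (ρ = 0.9). This is favourable because it allows no decay over time.
- 0.85/0.75/0.70: reduction 3.2%, half-width 3.23.
- 0.90/0.80/0.75: reduction 1.3%, half-width 3.26.
- 0.90/0.80/0.72: p = 0 because 0.90 × 0.80 = 0.72, so there is no gain.

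**Finite-sample cost.** Simulated trials with 41 per arm (6,000 per scenario):

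| Correlations | Mean CI-width ratio, two covariates to one | Trials with a narrower CI |
|---|---|---|
| 0.80/0.80/0.80 | 0.900 | over 99.9% |
| 0.85/0.75/0.70 | 0.988 | 72% |
| 0.90/0.80/0.75 | 0.998 | 47% |
| 0.80/0.80/0.64 (no added information) | 1.004 | 21% |

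**The case against.** The strongest reply is that nothing is wrong. An ANCOVA on one baseline is valid for the treatment contrast, and the model, the baseline rule and the endpoint definition agree with each other. That stands. A reader might infer bias because Day 1 BCVA also serves for eligibility and for choosing the worse eye. The documents do not support that: both steps precede randomization and apply equally to all arms.

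A reader might also infer that the final analysis omits Screening BCVA. That cannot be shown, because the SAP governs and its covariate list is redacted. The silence of SAP section 16 suggests, but does not prove, that the Protocol model stands. Nor is the Screening value thrown away: it decides eligibility and becomes the baseline if Day 1 is missing or invalid.

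The size is open to challenge too. The upper end needs large test-retest error and no true change between Screening and Day 1, and the documents bound neither. Where correlation decays with time the gain can be 1% to 3% of variance, or nil. There is a counterpoint: under the measurement-error model, a zero gain cannot occur while Day 1 carries independent error. That supports expecting some gain, but not a particular amount.

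Finally, this is an exploratory Phase 2a trial with more power than it states at its own inputs, so there is no power shortfall to repair.

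**Conclusion.** The point holds as an efficiency suggestion. It is firm for the Protocol's primary ANCOVA and the visible MMRM, and conditional on the unredacted model for SAP 13.1. A scheduled pre-randomization BCVA reading is not used as a covariate, and adding it would be legitimate.

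The plausible reduction in residual variance is about 0% to 20%: 4% to 20% at test-retest SD 3 to 5 letters with true Screening-to-Day 1 change SD up to 3, and 1% to 4% at test-retest SD 2. The half-width would then lie between about 3.28 and 2.93 letters. Every figure in this range except the 7.5-letter SD and the 41 per arm rests on an assumption.

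It would be tempting to say that the covariate narrows the comparison for certain and at no cost. The documents do not support that, since the deciding partial correlation is not given and one degree of freedom is spent. The likely benefit still outweighs the worst average loss of about 0.4% in CI width. The gain in the MMRM was not computed separately.

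**What to change.** First confirm the covariate list in the unredacted SAP 13.1. If Screening BCVA is not already there, amend SAP 13.1 and 13.2 before unmasking:
- Add study-eye Screening BCVA letter count as a second continuous covariate in the primary ANCOVA and in the MMRM.
- Keep Day 1 as the reference for change from baseline.
- For rescreened subjects, use the last Screening reading before Day 1.
- State a simple rule for a missing or invalid Screening value, and for a subject whose baseline is itself the Screening value. One option is to impute the mean of the pre-randomization Screening values, taken over all arms.
- Record the change in SAP section 16.

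The cost is a short SAP amendment and one degree of freedom (119 to 118). No new data are needed. The same step with the reading center's Screening CST in the CST models is optional; no size has been worked out for it.

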8.5.2 Secondary Efficacy Analyses

The secondary efficacy endpoints are:

- Change from baseline in CST as measured by Spectral Domain OCT (SD-OCT)
- Proportion of eyes with a ≥ 2 step improvement from baseline in DRSS score
- Change from baseline in BCVA letter count as measured by ETDRS
- Proportion of study eyes with ≥ 5 , ≥ 10 , and ≥ 15 BCVA letter change from baseline (gain and loss).

Change from baseline in BCVA letter count in the study eye at Week 24 and change from baseline in CST in the study eye as measured by SD-OCT at Week 16 and Week 24 will be analyzed using the same method described for the primary efficacy analysis. Note that change from baseline in CST will be in favor of KVD001 if the treatment difference is < 0 .

The proportion of study eyes with improvement of 2 or more steps on the ETDRS DRSS score between the sham procedure group and each of the KVD001 injection groups will be summarized by visit using discrete summary statistics, including 95% asymptotic normal CIs for each treatment group. The difference in proportions between each of the KVD001 groups and the sham procedure group will be analyzed at Week 16 and Week 24 using a Pearson's chi-squared test. 95% asymptotic normal CIs for the differences in proportions will also be calculated. Fisher's exact tests and exact CIs will be employed in cases of expected counts < 5 .

The proportion of study eyes with ≥ 5 , ≥ 10 and ≥ 15 BCVA letter change (gain and loss) between baseline and Weeks 16 and 24 will be analyzed using the same method described for the proportion of study eyes with improvement of 2 or more steps on the ETDRS DRSS score.

8.6 Safety Analyses

Safety endpoints include AEs, manifest refraction/BCVA, slit lamp biomicroscopy, dilated ophthalmoscopy, IOP, SD-OCT, ETDRS DRSS, physical exam findings, laboratory test results, and vital signs.

8.6.1 Adverse Events

AEs will be coded using the MedDRA dictionary. Frequencies and percentages of subjects with treatment-emergent adverse events (TEAEs), serious TEAEs, and TEAEs causing premature discontinuation will be provided by treatment group. An AE is treatment emergent if it 1) occurs after the first dose of randomized study treatment or 2) if it is present prior to receipt of randomized study treatment but worsens in severity or increases in frequency after the first dose of randomized study treatment. Furthermore, frequencies will be given of subjects with TEAEs by system organ class and preferred term; by system organ class, preferred term and maximal severity; by system organ

class, preferred term and strongest relationship; by system organ class and preferred term for SAEs; and by system organ class, preferred term, and day of onset. Separate analyses will be performed for ocular specific and all AEs (including systemic). AEs will be classified by System Organ Class (SOC) and preferred term in the MedDRA coding dictionary. AEs will be tabulated both as the total events (regardless of relationship to treatment) and as drug-related events. The number of subjects with one or more events versus no events will be calculated for each treatment.

Subject listings of all AEs will be provided as well as listings of deaths, SAEs, and AEs leading to discontinuation.

The following summaries will be provided:

- Relationship between AE SOC and verbatim text;
- On-treatment AEs: number and percentage of subjects reporting each AE, each AE leading to withdrawal, each SAE, each drug-related SAE, each fatal AE, and most frequent by treatment;
- Post-treatment AEs: number and percentage of subjects reporting each AE;
- Listing of all AEs;
- Summary of Most Frequent AEs.

8.6.2 Laboratory Assessments

Laboratory assay results include hematology, clinical chemistry, liver enzymes, electrolytes, and urinalysis. Each of the continuous parameters will be summarized using continuous descriptive statistics for each treatment group and for all subjects at each visit. Changes from baseline will also be summarized for each treatment group and for all subjects where appropriate. Each categorical parameter will be summarized using frequency counts and percentages for each treatment group and for all subjects. A shift table of the changes from baseline will also be presented.

The high/low criteria will be determined based on the reference ranges provided by the laboratory. The actual values and change from baseline values for each laboratory assessment will be summarized by treatment group. Summaries of assessments outside the normal range and the changes from baseline relative to the normal range will also be produced. A subject listing of laboratory assessments will also be produced and will include changes from baseline at each visit. Data from subjects who have values outside the normal range will be specified in this listing.

8.6.3 Vital Signs

Vital sign measurements, including pulse, respiratory rate, blood pressure (SBP, DBP), body temperature, height, weight and BMI, will be summarized by visit and time point using continuous descriptive statistics for each treatment group and for all subjects. Change from baseline to each visit will also be summarized for each treatment group and for all subjects. Systolic and diastolic BP, heart rate, respiration rate, and body temperature will be summarized by treatment group at each visit and for the maximum/minimum post-baseline. The change from baseline values will also be summarized. A subject listing will also be produced and will include changes from baseline at each visit.

8.6.4 Physical Examination

A subject listing of the Visit 1 (Screening) physical examination findings will be produced.

8.6.5 Slit Lamp Biomicroscopy

A slit-lamp biomicroscopy examination of the cornea, conjunctiva, anterior chamber, iris/pupil, lens, and eyelid will be performed at each visit. The findings will be graded as normal or abnormal [non-clinically significant (NCS) or clinically significant (CS)]. The findings will be summarized for each treatment group and for all subjects at each visit for each eye (study eye and fellow eye). The findings will be summarized using counts and percentages for each treatment group and for all subjects combined at each visit for each eye (study eye and fellow eye). Shift tables for the slit-lamp biomicroscopy parameters will also be provided comparing each follow-up visit to baseline. A subject listing of the slit-lamp biomicroscopy examination parameters will also be produced.

8.6.6 Indirect Dilated Ophthalmoscopy

A dilated ophthalmoscopy examination of the vitreous, macula, optic nerve, peripheral retina, and choroid will be performed at each visit. The findings will be graded as normal or abnormal (NCS or CS). The findings will be summarized using frequency counts and percentages by treatment group and for all subjects at each visit for each eye (study eye and fellow eye). A shift table of changes from baseline will also be presented. Cup-to-disc ratio is also reported for each visit and will be summarized using continuous descriptive statistics. Change from baseline will also be summarized by treatment group for each eye (study eye and fellow eye). A subject listing of the dilated ophthalmoscopy examination parameters will also be produced.

8.6.7 Intraocular Pressure

IOP of both eyes will be assessed. IOP will be summarized using continuous descriptive statistics for each treatment group and for all subjects at each visit for each eye (study eye and fellow eye). Change from baseline will also be summarized for each treatment group for each eye (study eye and fellow eye). Categorical summary statistics will also be presented using the following categories: ≤ 5 , 6 to 14, 15 to 21, 22 to 29, and ≥ 30 mmHg for each visit and using the following categories: ≤ -15 , -14 to -10, -9 to -5, -4 to 0, 1 to 4, 5 to 9, 10 to 14, 15 to 19, and ≥ 20 mmHg for change from baseline to each visit. A subject listing of IOP will also be produced.

8.6.8 Best Corrected Visual Acuity and Manifest Refraction

Best-Corrected visual acuity of both eyes will be measured consistent with the standard procedure developed for the ETDRS. The number of letters read correctly will be counted and the total BCVA letter score will be reported. The total BCVA letter score will be summarized for each treatment group using continuous descriptive statistics at each visit for each eye (study eye and fellow eye). Change from baseline will also be summarized by treatment group and visit for each eye (study eye and fellow eye).

The number of subjects (by eye) with a gain or loss in BCVA letter score ≥ 15 , ≥ 10 , and ≥ 5 from baseline will be summarized using counts and percentages for each treatment group at each visit.

A subject listing of BCVA and manifest refraction will also be produced.

